12.4. Appendix 4: Collection of Pregnancy Information

Collection of Pregnancy Information

Female Participants who become pregnant

- Investigator will collect pregnancy information on any female participant, who becomes pregnant while participating in this study.
- Information will be recorded on the appropriate form and submitted to GSK within 24 hours of learning of a participant's pregnancy.
- Participant will be followed to determine the outcome of the pregnancy. The investigator will collect follow up information on participant and neonate, which will be forwarded to GSK Generally, follow-up will not be required for longer than 6 to 8 weeks beyond the estimated delivery date.
- Any termination of pregnancy will be reported, regardless of fetal status (presence or absence of anomalies) or indication for procedure.
- While pregnancy itself is not considered to be an AE or SAE, any pregnancy complication or elective termination of a pregnancy will be reported as an AE or SAE.
- A spontaneous abortion is always considered to be an SAE and will be reported as such.
- Any SAE occurring as a result of a post-study pregnancy which is considered reasonably related to the study treatment by the investigator, will be reported to GSK as described in [Appendix 3](#). While the investigator is not obligated to actively seek this information in former study participants, he or she may learn of an SAE through spontaneous reporting.

Any female participant who becomes pregnant while participating

- Will be withdrawn from the study.

## 1. INTRODUCTION

The purpose of this reporting and analysis plan (RAP) is to describe the analyses to be included in the Clinical Study Report for Protocol:

Revision Chronology:		
2016N305948_00	27 - FEB - 2017	Original
2016N305948_01	17 - MAY - 2017	Amendment 01 was created to make the following changes: to extend the time a participant must not have used the ELLIPTA, DISKUS, or HandiHaler inhalers prior to Visit 1, to delete one of the withdrawal criteria, to add an exclusion criteria for participants that are only taking a SABA, and to add some clarification to the overall study design. One additional endpoint was added to assess inhaler regimen preference based on the number of steps needed to take the medication.

## 2. SUMMARY OF KEY PROTOCOL INFORMATION

### 2.1. Changes to the Protocol Defined Statistical Analysis Plan

There were no changes or deviations to the originally planned statistical analysis specified in the protocol amendment 1 [(Dated: 17/MAY/2017)].

### 2.2. Study Objective(s) and Endpoint(s)

Objectives	Endpoints
Primary Objectives	Primary Endpoints

 
To evaluate the relative proportions of COPD participants who correctly use an ELLIPTA inhaler compared to those who correctly use a DISKUS + HandiHaler combination to receive their COPD medications.
 
	
 
Comparison of correct inhaler use as defined by the percentage of participants with zero errors after 28 days of use.
 

Secondary Objectives	Secondary Endpoints

 
To evaluate the overall correct use of an ELLIPTA inhaler compared to the DISKUS + HandiHaler combination in COPD participants
 
	
 
Number of errors by type for each inhaler after 28 days of use
 
Number and change in errors per participant for each treatment group (V2 and V3) after 28 days of use.
 
Number and change in errors for each treatment group in participants with one or more errors after 28 days of use.
 

 
To evaluate the relative proportions of
 
	
 
Comparison of correct inhaler use as defined
 

Objectives	Endpoints
critical errors for COPD participants using an ELLIPTA inhaler compared to those using a DISKUS and HandiHaler to receive their COPD medications.	by the percentage of participants with zero critical errors after 28 days of use.
Other Objectives	Other Objectives

 
To evaluate the impact of number of COPD maintenance inhalers on study inhaler errors (ELLIPTA and DISKUS + HandiHaler) after 28 days of use.
 
	
 
Comparison of correct inhaler use as defined by the percentage of participants with zero errors after 28 days of use, including the number of prescribed maintenance inhalers as a covariate.
 

 
To evaluate the number of overall errors made by COPD participants after a participant has read the Patient Instruction Leaflet (PIL(s)).
 
	
 
The comparison of participants making zero errors after reading the PIL (s) at the start of each treatment period.
 


 
To evaluate the participant's preference of these inhaler options based on how easy it was to tell how many doses were remaining.
 
	
 
Inhaler preference based on how easy it was to tell how many doses remain.
 

 
To evaluate inhaler preference of taking a regimen that was one inhaler, once a day versus multiple inhalers with a varied dosing regimen.
 
	
 
Inhaler dosing regimen preference.
 

 
To evaluate whether more participants with COPD prefer the ELLIPTA inhaler to the DISKUS + HandiHaler combination inhalers regimen based on the number of steps needed to take the medication.
 
	
 
Inhaler regimen preference based on the number of steps needed to take the medication.
 

### 2.3. Study Design

Overview of Study Design and Key Features	

The diagram illustrates the study timeline. It features three vertical arrows pointing downwards, labeled 'Day 1: V1', 'Day 28: V2', and 'Day 56: V3'. Below these arrows are two horizontal bars representing treatment periods. The top bar is blue and spans the entire duration from Day 1 to Day 56. The bottom bar is green and is divided into two segments: 'INHALER 1' (from Day 1 to Day 28) and 'INHALER 2' (from Day 28 to Day 56). Below the bars, three key events are listed: 'Day 1 Training Inhaler 1', 'Day 28 Training Inhaler 2 Correct Use Inhaler 1', and 'Day 56 Correct Use Inhaler 2 Preference'.
	
Design Features	
The study will be conducted as a multi-centre, randomised, open-label, placebo-device, cross-over study, with a 2x2 complete block design.
 
This study has 3 visits and will be completed in approximately 56 days. COPD diagnosed participants will attend the clinic for the screening visit (V0) and subsequent assessment visit (V1). These visits may occur on the same day.
 
There is no active treatment and participants will continue to take their own prescribed COPD maintenance medication and rescue medications during the entire 56-day study period.
 
The treatment groups are the following:
 
 
• At Visit 1 (Day 1) half of the participants will be randomized to receive a placebo ELLIPTA (QD) inhaler for use during the first 28 day treatment period. The remaining half of the participants will receive a placebo DISKUS (BID) + placebo HandiHaler (QD) for use during the first 28 day treatment period.
 
• At Visit 2 (Day 28) participants previously receiving the placebo DISKUS + placebo HandiHaler inhalers at Visit 1 will receive a placebo ELLIPTA (QD) inhaler for the second 28 day treatment period. Those participants initially receiving a placebo ELLIPTA inhaler at Visit 1 will receive a placebo DISKUS (BID) inhaler + a placebo HandiHaler (QD) inhaler for the second 28 day treatment period.
 
• At Visit 3 (Day 56) after conducting their last correct inhaler use assessments, participants will answer either preference questionnaire 1 or preference questionnaire 2 depending on their randomization schedule.
 

Dosing	
 
• Not applicable as this is a placebo study.
 

Overview of Study Design and Key Features				
Time & Events	
 
Refer to Appendix 2: Schedule of Activities
 
			
Treatment Assignment	Sequence	Period 1	Period 2	Preference Questionnaire
	A	ELLIPTA	DISKUS + HandiHaler	1
	B	ELLIPTA	DISKUS + HandiHaler	2
	C	DISKUS + HandiHaler	ELLIPTA	1
	D	DISKUS + HandiHaler	ELLIPTA	2

## 2.4. Statistical Hypotheses / Statistical Analyses

The primary purpose of this study is to assess the number of errors made by COPD participants, for the ELLIPTA inhaler or DISKUS + HandiHaler inhalers combined after 28 days use. This is a superiority study.

The primary endpoint is the percentage of participants making zero errors on the ELLIPTA inhaler compared with the DISKUS + HandiHaler inhalers.

The null hypothesis is that there is no difference in the proportion of participants making zero errors on the ELLIPTA inhaler compared to the DISKUS + HandiHaler inhalers.

$$H_0: P_E - P_{D+H} = 0$$

The alternative hypothesis is there is a difference in the proportion of participants making zero errors on the ELLIPTA inhaler compared to the DISKUS + HandiHaler inhalers.

$$H_1: P_E - P_{D+H} \neq 0$$

### 3. PLANNED ANALYSES

#### 3.1. Final Analyses

No interim analysis is planned.

The final planned primary analyses will be performed after the completion of the following sequential steps:

1. All subjects have completed the study as defined in the protocol.
2. All required database cleaning activities have been completed and final database release has been declared by Data Management.
3. All criteria for unblinding the randomisation codes have been met.
4. Randomisation codes schedule have been distributed according to RandAll NG procedures.
5. Database freeze has been declared by Data Management.

### 4. ANALYSIS POPULATIONS

Population	Definition / Criteria	Analyses Evaluated
All Subjects Enrolled (ASE)	
 
• All participants who sign the ICF and for whom a record exists in the study database, including screen failures and any participant who was not screened but experienced an SAE between the date of informed consent and the planned date of the Screening visit.
 
	
 
• Study population
 
• Subject disposition
 
• Reason for withdrawal prior to randomisation
 
• Inclusion, exclusion and randomisation criteria deviations
 

Intent-to-treat (ITT)	
 
• All randomised participants, excluding those who were randomised in error, and did not have at least one error assessment at Visit 1. A participant who is recorded as a screen failure or run-in failure and also randomised will be considered to be randomised in error. Any other participant who receives a randomisation number will be considered to have been randomised. This population will be analysed according to the randomised sequence order and not the sequence order they actually followed.
 
	
 
• Study population
 
• Efficacy
 

Safety	
 
• This population will be the same as the Intent-to-Treat population.
 
	
 
• Safety
 

#### NOTES :

- Please refer to [Appendix 10](#): List of Data Displays which details the population to be used for each displays being generated.

## 4.1. Protocol Deviations

Important protocol deviations (including deviations related to study inclusion/exclusion criteria, conduct of the trial, patient management or patient assessment) will be summarised and listed.

Protocol deviations will be tracked by the study team throughout the conduct of the study in accordance with the Protocol Deviation Management Plan Version 1 (07-Jul-2017) or later.

- Data will be reviewed prior to freezing and unblinding the database to ensure all important deviations are captured and categorised on the protocol deviations dataset.
- This dataset will be the basis for the summaries and listings of protocol deviations.

A separate summary and listing of all inclusion/exclusion criteria deviations will also be provided. This summary will be based on data as recorded on the inclusion/exclusion page of the eCRF.

## 5. CONSIDERATIONS FOR DATA ANALYSES AND DATA HANDLING CONVENTIONS

### 5.1. Study Treatment & Sub-group Display Descriptors

Treatment Group Descriptions			
RandAll NG		Data Displays for Reporting	
Code	Description	Description	Order [1]
A	ELLIPTA Inhaler	ELLIPTA	1
B	DISKUS Inhaler + HandiHaler Inhaler	DISKUS + HandiHaler	2
Q1	Preference Questionnaire 1	Questionnaire 1	3
Q2	Preference Questionnaire 2	Questionnaire 2	4

#### NOTES:

1. Order represents treatments being presented in TFL, as appropriate.

### 5.2. Multicentre Studies

In this single country study, enrolment will be presented by investigative site.

### 5.3. Examination of Covariates, Other Strata and Subgroups

#### 5.3.1. Covariates and Other Strata

The list of covariates and other strata may be used in descriptive summaries and statistical analyses. Additional covariates and other strata of clinical interest may also be considered.

Category	Covariates and / or Subgroups
Number of prescribed maintenance inhalers	This will be included as a covariate in the model to examine whether additional background inhalers impact error rates. Number of prescribed maintenance inhalers will be fitted as a categorical variable.

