10.2. Sample Size Determination

The sample size calculations for this study have been based on the primary endpoint, which is the percentage of participants making zero errors in each treatment group (ELLIPTA or DISKUS + HandiHaler) after 28 days use.

The estimates of inhaler errors were taken from the overall errors reported in the 200301 study for each individual inhaler (ELLIPTA, DISKUS and HandiHaler) separately. Although this study is only assessing combined errors in the DISKUS + HandiHaler treatment group, individual inhaler errors were used to estimate the combined error rate in order to provide a conservative estimate. By doing this it assumes that participants, who made no errors on the DISKUS inhaler, would not make any errors of the HandiHaler inhaler and vice-versa.

As the 200301 study only had a single visit, no estimates were available for error rates over 28 days, however the study did provided estimates of participant errors after reading the PIL and after being instructed on correct use by a HCP up to three times. As participants will have the PIL for 28 days, and can be instructed by a HCP at the inhaler dispensing visit if necessary, both estimates of error rates along with a sensitivity analysis examining some of the potential error rates between were used to inform sample size calculations.

Using 10,000 simulations, a total of 216 participant (54 per treatment sequence) provide at least 90% power to show a statistically significance difference between the overall error rate of the ELLIPTA inhaler versus DISKUS + HandiHaler inhalers, for all of the paired treatment error rates shown in [Table 1](#).

Table 1 Error rates of ELLIPTA vs. DISKUS + HandiHaler achievable with 90% power, 5 % Type 1 error using a total of 216 participants

ELLIPTA Error Rate	DISKUS + HandiHaler Error Rate
33%	>=50%
30%	>=47%
20%	>=35%
10%	>=23%
5%	>=15%

Conditional logistic regression and a two-sided 5% significance level were used as the analysis method for all simulations performed. As it is expected that some participants would drop out or change inhalers during the study, with 10% withdrawal it would be

necessary to enrol 240 participants (60 per treatment sequence) to ensure there were 216 participants with evaluable data at the end of the study.

For the purpose of this study an evaluable participant is defined as a randomized participant who completed error assessments for both randomized treatment groups.

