**7.3.2. Summary Measure**

- 1) Odds ratio and p-value for interaction
- 2) Odds ratio
- 3) Summary statistics and p-value
- 4) Summary statistics and p-value
- 5) Summary statistics and p-value

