#### 7.3.5.1. Statistical Methodology Specification

Endpoint / Variables

 
Comparison of correct inhaler use as defined by the percentage of participants with zero errors after 28 days of use, including the number of prescribed maintenance inhalers as a covariate.
 

Model Specification

 
The primary endpoint of the percentage of participants with zero errors after 28 days of use, will be analysed using the Intent-to-treat population.
 
This endpoint will be analysed using conditional logistic regression with subject as fixed strata. Treatment option, number of COPD maintenance devices and period will be fixed effects.
 
Two models will be analysed. The first will contain the number of COPD maintenance devices and treatment option, whilst the second will include the interaction term between the number of COPD maintenance devices and treatment option.
 
If there are low cell counts (<5) in the cross tabulation of subjects making errors on ELLITPA compared to DISKUS + HandiHaler or the model fails to converge with all cell counts >=5, then the exact conditional logistic regression with subject as fixed strata, and treatment option and period as fixed effects will be used instead.
 

Model Checking & Diagnostics

 
See Section 7.1.5.1.
 

Model Results Presentation

 
See Section 7.1.5.1. In addition, for the interaction model the p-value for the interaction will also be produced.
 

Sensitivity and Supportive Analyses

 
No sensitivity analysis will be performed.
 

Endpoint / Variables

 
The comparison of participants making zero errors after reading the PIL (s) at the start of each treatment period
 

Model Specification

 
See Section 7.1.5.1.
 

Model Checking & Diagnostics

 
See Section 7.1.5.1.
 

Model Results Presentation

 
See Section 7.1.5.1.
 

Sensitivity and Supportive Analyses

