**10.6.2.3. Number of maintenance COPD****Number of maintenance COPD inhalers**

The covariate of number of maintenance COPD inhalers will be calculated using the CONMED page in the eCRF.

To calculate this all inhaled medications will be counted if:

- They were delivered by a device for  $\geq 4$  weeks prior to randomisation (as per inclusion criteria in the protocol)
- The subject was still using the device at the time of randomisation
- The reason for medication is 'COPD'
- The frequency is not 'PRN' as this is used to denote rescue medications

These devices will then be summed in order to find the total number of COPD maintenance inhalers per subject..

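### The exploratory interaction model fits the raw inhaler count as ungrouped categories, which is fragile if a few participants have three or more inhalers, and its exact fallback omits the interaction

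*SAP*

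**What the plan says.** SAP 5.3.1 names one covariate and fixes its coding: "Number of prescribed maintenance inhalers will be fitted as a categorical variable". SAP 10.6.2.3 counts inhaled COPD medications that were used for at least 4 weeks before randomisation, were still in use then, and are not taken as needed. It then says "These devices will then be summed in order to find the total number of COPD maintenance inhalers per subject". Neither section caps the count or merges levels.

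SAP 7.3.5.1 fits two conditional logistic models with participant as stratum. The first has the count and treatment, "whilst the second will include the interaction term between the number of COPD maintenance devices and treatment option". SAP 7.3.2 gives the summary measure as "Odds ratio and p-value for interaction", and Table 2.16 adds a row for that p-value. The type of test (Wald, likelihood ratio or score) is not named.

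The same section has a fallback to exact conditional logistic regression. It is triggered by a cell below 5 in the overall cross-tabulation of errors on the two regimens, or by failure to converge. The exact model lists treatment and period as its fixed effects. Neither the count nor the interaction is listed. Model checking is stated as none, by reference to 7.1.5.1.

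**The concern.** In a two-period model stratified by participant, only participants with an error on one regimen and none on the other contribute. Each observed inhaler count needs its own device log-odds ratio from the discordant participants at that count. With no discordant pair at a count, that term drops out. If all its discordant pairs point the same way, the estimate is infinite. An infinite term has a huge standard error, so a joint Wald test spends a degree of freedom on it and gains almost nothing.

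The count is constant within a participant, so its main effect cancels from the conditional likelihood whatever the coding. The interaction is therefore the only model term that can address the objective on number of maintenance inhalers. If its p-value is unreliable, or the fallback removes it, that objective has no inferential answer.

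**Working it through.** **Inputs from the documents.** Protocol 10.2: "Conditional logistic regression and a two-sided 5% significance level were used as the analysis method for all simulations performed"; 216 evaluable participants; Table 1 error rates (ELLIPTA / DISKUS + HandiHaler) of 33/50, 30/47, 20/35, 10/23 and 5/15%; 10% withdrawal.

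**Assumptions.** The documents do not give the share of participants at each count, the size of any interaction, or the correlation between errors on the two regimens. Errors are taken as independent unless stated.

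**1. The plan's own figure.** The protocol says: "Using 10,000 simulations, a total of 216 participant (54 per treatment sequence) provide at least 90% power". Simulating 10,000 trials per Table 1 row, with treatment and period in the model, gives Wald power of 94.6, 95.2, 93.6, 95.7 and 92.4%. The claim is reproduced in every row, and 216/(1 − 0.10) = 240. The documents state no power for the interaction.

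**2. Discordant pairs.** Let a = pD(1 − pE) be the chance of an error on DISKUS + HandiHaler only, and b = pE(1 − pD) the chance of an error on ELLIPTA only. The expected number of discordant pairs is 216(a + b):
- 33/50: a = 0.335, b = 0.165, giving 108
- 10/23: a = 0.207, b = 0.077, giving 61
- 5/15: a = 0.1425, b = 0.0425, giving 40

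A level holding 2% of participants then has about 2.2, 1.2 or 0.8 discordant pairs.

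**3. Chance that one level fails.** For a level with share s, the chance that it is observed but has no discordant pairs, or only one-directional ones, is

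(1 − sa)^216 + (1 − sb)^216 − (1 − s(a + b))^216 − (1 − s)^216.

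For s = 0.02 at 33/50: 0.234 + 0.490 − 0.114 − 0.013 = 0.597.

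| Share of level | 33/50 | 10/23 | 5/15 |
|---|---|---|---|
| 2% | 60% | 82% | 91% |
| 5% | 19% | 49% | 71% |
| 15% | 0.5% | 8% | 26% |
| 40% | 0% | 0.1% | 2% |

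Simulated trials without interaction agree. At least one level fails in 59, 83 and 91% for counts 1/2/3 split 60/38/2%, and in 19, 55 and 82% for 1/2/3/4 split 50/30/15/5%. With errors correlated within participant (random-intercept SD 1), a 70/25/5 split gives 29% at 33/50 and 36% at 20/35. With two levels only (60/40) it is 0 to 2%.

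**4. Size of the test without interaction** (1,000 trials per setting, nominal 5%; 33/50, 10/23, 5/15).
- 60/38/2: ungrouped Wald 1.7, 1.8, 1.2%; ungrouped likelihood ratio 4.9, 4.6, 5.8%.
- 50/30/15/5: ungrouped Wald 2.0, 0.8, 0.2%; ungrouped likelihood ratio 6.0, 6.6, 7.5%.

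**5. Power for a 3-fold ratio of device odds ratios, one versus two or more inhalers** (same order of error rates).

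| Split, test | Ungrouped | Grouped, 1 vs ≥2 |
|---|---|---|
| 70/25/4/1, Wald | 25, 6, 1% | 62, 36, 13% |
| 70/25/4/1, LR | 54, 33, 20% | 66, 45, 29% |
| 50/30/15/5, Wald | 44, 14, 2% | 75, 47, 26% |
| 50/30/15/5, LR | 60, 37, 22% | 75, 49, 30% |
| 60/38/2, LR | 63, 39, 28% | 71, 48, 34% |

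For a 2-fold ratio, grouped likelihood-ratio power is only about 13 to 39%. The loss from not grouping can then be as small as 2 points (60/38/2 at 5/15: 14.4 versus 16.2%).

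**6. The fallback.** The below-5 check uses the overall table, so a sparse inhaler level does not trigger it. It can fire for another reason. The expected number with errors on both regimens is 216 × 0.33 × 0.50 = 36 at 33/50, 216 × 0.10 × 0.23 = 5.0 at 10/23, and 216 × 0.05 × 0.15 = 1.6 at 5/15. At low error rates the switch to the exact model is therefore likely, unless errors are strongly correlated. That model, as written, has no interaction term.

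**The case against.** The strongest objection is that sparsity is assumed. The protocol's background section describes separate-inhaler triple therapy as an ICS/LABA plus a LAMA, which is two devices, and the derivation leaves out as-needed inhalers. Counts might be almost entirely 1 and 2, and then ungrouped coding is already the grouped coding. This stands: nothing in the documents shows how common three or more inhalers are. Nothing excludes them either, and a pre-specified rule should not depend on their absence.

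The large power losses need a Wald test, which the SAP does not name. This also stands. With a likelihood-ratio test the loss is moderate and size is near nominal.

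The fallback has a second trigger, non-convergence, which one-directional levels may set off. That is correct, so the SAP is not blind to the problem. But the model it then switches to omits the interaction.

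Grouping narrows the question from number of inhalers to one versus several, and the power comparison above puts the true effect exactly at that cut. This is fair. If the effect rises steadily with each inhaler and 15% have three or more, the advantage of grouping may shrink to about nothing.

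Finally, the endpoint is exploratory, with no power target or decision rule. That limits the consequence.

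**Conclusion.** The point holds conditionally. The ungrouped coding, the unnamed test and the fallback without an interaction term are all in the text. The numerical harm depends on an assumed distribution of counts. With 2-5% in the rarest level, a level fails in roughly 30-90% of null trials (19% in the mildest setting), a Wald test is conservative at about 1-2%, and a likelihood-ratio test usually loses about 5 to 16 points of power. With only counts 1 and 2 there is almost no problem.

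A reader might infer more, and the documents do not support it:
- That the interaction test has almost no power. This fits only a Wald test with sparse levels and low error rates or small interactions. Likelihood-ratio power for a 3-fold ratio was 20 to 63% ungrouped in the settings tabulated.
- That the coding explains the low power. Much of it comes from sample size and remains after grouping.
- That a count of 0 is to be expected. Inclusion criteria 7 and 8 and exclusion criterion 4 make it unlikely. It could arise only through the derivation, for example non-inhaled maintenance or an inhaler recorded as needed.
- That the SAP will read a non-significant result as no effect. It does not say so.

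The primary analysis and the sample size are unaffected.

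**What to change.** Amend SAP 5.3.1, 7.3.5.1 and 10.6.2.3 as follows:
- For the interaction model, fit the number of maintenance inhalers in two pre-specified groups, ≤1 versus ≥2, giving a 1-degree-of-freedom interaction test.
- Take the interaction p-value from a likelihood-ratio test, or from the exact test when the fallback applies. Grouping alone is not enough: the grouped Wald test still rejected only 2.0 to 2.9% under no interaction at 5/15 in the 60/38/2 and 50/30/15/5 splits.
- State that the exact fallback for this model keeps the group-by-treatment term.
- Show errors by ungrouped count descriptively.
- Add a note to Table 2.16 that a non-significant interaction is not evidence of no effect.

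The cost is a few sentences of SAP text and no new data. The downside is that two inhalers and three or more are no longer separated in the model.
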